Population Level Summary: Hazard ratios (HRs) associated with potential risk factors and modifiers to the HR for the treatment effect comparing HCQ vs. placebo will be estimated with 95% CIs based on a Cox proportional hazards model.	
Analysis: In the first step in the analysis, fixed effect characteristics of participants who developed CL-RA will be compared to those who did not develop CL-RA during the study using descriptive (e.g., means (SD) or n (%)) and inferential statistics (e.g., Mann-Whitney or Fisher-type exact statistics) appropriate for the nature of the variable.
 
In the next step, the impact of potential risk factors on the development of RA and modification of the treatment effect will be explored using a Cox proportional hazards model. To identify a subset of risk factors for possible inclusion in a final model, we will first run preliminary models each with one potential risk factor, treatment, and the treatment*risk factor interaction. Risk factors with p-values <0.1, and interaction terms with p-values <0.05 will be considered for the final model. The same criteria for inclusion will be used for the final model. Interaction terms will be evaluated first, dropping least significant terms one-by-one until only interactions with p<0.05 remain. Fixed effect components of interaction terms will be included in the final model regardless of p-value. For other fixed effect terms, least significant terms will be dropped one-by-one until only terms with p<0.1 remain. Note: The validity of the proportional hazards assumption will be evaluated.
 
Finally, if results of analyses described in Section 8.3.6, Study Objective 7 or Section 8.3.7, Study Objective 8 suggest that evolving symptoms or risk factors are potentially related to the development of CL-RA, we will consider adding time-varying covariates to the model developed above. The modeling approach will follow that outlined above. Time-varying covariates must be carefully defined prior to modeling, and models must be interpreted with caution.
 
Note: The time-varying covariate model will be exploratory and only undertaken if warranted by results of other analyses.

Fixed effects (i.e., potential risk factors) to be evaluated include:

- Study site (Colorado vs other sites)
- Method of recruitment (FDR, Population-based screening, rheumatology clinic)
- Baseline self-reported joint pain
- Baseline self-reported joint stiffness
- Baseline self-reported joint swelling

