- Baseline self-reported fatigue
- Baseline CDAI
- Baseline SDAI
- Baseline RAPID-3
- Baseline DAS28-CRP

Autoimmunity Centers of Excellence
Statistical Analysis Plan – ARA08 StopRA

- Baseline PROMIS Profile 29 Physical Health Score
- Baseline PROMIS Profile 29 Mental Health Score
- Baseline PROMIS Profile 29 Social Health Score
- Baseline Anti-CCP3 (units)
- Baseline Anti-CCP3 Positivity (Negative (< Upper Limit of Normal (ULN), Low Positive (1.0 - <2.0 x ULN), Medium Positive (2.0 - <3.0 x ULN), High Positive (\geq 3.0 x ULN))
- Baseline IgM-RF (U/mL)
- Baseline IgM-RF Positivity (Negative (< Upper Limit of Normal (ULN), Low Positive (1.0 - <2.0 x ULN), Medium Positive (2.0 - <3.0 x ULN), High Positive (\geq 3.0 x ULN))
- Baseline hs-CRP (mg/L)
- Baseline hs-CRP Positivity (\leq 3.0 mg/L, $>$ 3.0 mg/L)
- Baseline age (years)
- Sex (male/female)
- BMI
- Baseline Shared Epitope (SE) Positivity (Yes, No)
- Baseline Shared Epitope Number of Positive Results (0, 1, 2)
- Participant has a FDR with RA (Yes, No)
- Salary level (< \$50,000; \$50,000 - < \$75,000; \geq \$75,000)
- Highest education level achieved (up to High School/GED, College, Graduate School)
- Tobacco exposure
 - Smoking status (Never smoked, Former smoker, Current smoker)
 - Baseline Pack Years at Current Level for Smokers
 - Years as Adult Living with Smoker
- Baseline Medications
 - Statin use (Yes/No)
 - Medical hormones (Yes/No)

Each fixed effect will be evaluated for its impact on the time to development of CL-RA by fitting a Cox proportional hazards model with independent variables for treatment arm, risk factor and treatment arm * risk factor interaction. The risk factors with significant p-values for the Wald chi-square test statistic, along with significant interaction terms, will be included in the final Cox proportional hazards model.

8.3.6. Study Objective 7

Study Objective 7 is to evaluate the relationship between treatment with HCQ and amelioration of symptoms of RA, and potential delay in onset of symptoms. RA symptoms include self-reported joint pain, stiffness, and swelling, and overall fatigue. The clinical endpoint to evaluate this objective will be the self-reported joint symptom counts assessed at each clinic visit.

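### Objective 6 picks its Cox model by p-value from 32 factors and 32 treatment interactions, then reports ordinary 95% confidence intervals that ignore the selection

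*SAP*

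**What the plan says.** Table 13 in SAP 8.3.5 covers risk factors for clinically-apparent RA and modifiers of the HCQ effect. Their hazard ratios "will be estimated with 95% CIs based on a Cox proportional hazards model". The model is reached in two steps.

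- **Screen.** Each factor gets its own model with treatment, the factor and their interaction. Then: "Risk factors with p-values <0.1, and interaction terms with p-values <0.05 will be considered for the final model".
- **Elimination.** Interactions go first, "dropping least significant terms one-by-one until only interactions with p<0.05 remain". For the other factors, "least significant terms will be dropped one-by-one until only terms with p<0.1 remain". The main effects that belong to a retained interaction stay whatever their p-value.

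The candidates follow the table ("Fixed effects (i.e., potential risk factors) to be evaluated include"), and each is tested with its treatment interaction. The paragraph closing the section words the rule differently. Significant risk factors, "along with significant interaction terms, will be included in the final Cox proportional hazards model", with no elimination step and no 0.1 cut-off.

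No shrinkage, resampling, selection-adjusted interval or multiplicity control is given. The estimand is labelled Secondary/Exploratory. SAP 8.1.4 treats secondary p-values and intervals as descriptive and makes no adjustment. Table 13 does urge cautious interpretation, but only for the later models with time-varying covariates.

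**The concern.** An ordinary 95% interval has its stated coverage when the term was going to be reported whatever the data showed. Here a term reaches the final model largely because its p-value was small in the same data. Its estimate is then biased away from the null and its interval is too optimistic.

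The ratio of candidates to data is also high: 32 factors plus 32 interactions make 64 terms, against about 65 expected events.

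Objective 6 is where the trial asks who progresses and who responds to HCQ. SAP 5.4 records that the DSMB recommended stopping early because of futility evidence. After that, a retained treatment interaction could easily be read as a subgroup that benefits, although the procedure often produces one when none exists.

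**Working it through.** **Inputs from the documents.** 144 randomized (interim SAP 5.2.2.1). 20% loss per arm, and a null case of 50% RA-free at 36 months in both arms (interim SAP Appendix 8.1). Exponential event times, 0.231 per year in controls (Protocol 8.1). Selection rules and candidate list from SAP 8.3.5.

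**Assumptions of mine.** 72 per arm, category frequencies, and the correlation among factors, which the documents do not give. I varied the correlation: independent, or symptom blocks at rho 0.3, 0.5 or 0.7 with paired continuous and categorical versions of the same marker.

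**Counting the candidates.** Site and recruitment method 2; self-reported symptoms 4; CDAI, SDAI, RAPID-3 and DAS28-CRP 4; PROMIS scores 3; anti-CCP3, IgM-RF and hs-CRP in two forms each 6; age, sex and BMI 3; shared epitope 2; relative with RA 1; salary and education 2; tobacco 3; medications 2. Total 32. The list is introduced as open-ended, so 32 is a minimum.

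**Expected events.** Loss rate = -ln(0.8)/3 = 0.0744 per year. Under the null, P(event) = 0.231/(0.231 + 0.0744) x (1 - 0.5 x 0.8) = 0.756 x 0.6 = 0.454, and 144 x 0.454 = 65 events. With the design effect (0.096 per year on HCQ), the HCQ arm has 0.096/(0.096 + 0.0744) x (1 - 0.75 x 0.8) = 0.563 x 0.4 = 0.225, so 72 x (0.454 + 0.225) = 49 events.

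**Calibration.** The plan states no error rate for Objective 6, so I checked the event model against the power figures in Protocol 8.1 for 80 per arm (20,000 simulated trials):

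| Case | Stated | Simulated |
|---|---|---|
| 50% vs 25% risk | 90% | 91.4% |
| Null | 4.6% | 4.7% |
| Hazard ratio 2.1 | 81% | 81.5% |
| 35% risk, hazard ratio 2.4 | 77% | 77.2% |

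**Closed form at the screen.** With 32 independent null interactions at 0.05, the expected number passing is 32 x 0.05 = 1.6, and P(at least one) = 1 - 0.95^32 = 80.6%.

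**Full Table 13 algorithm.** 2,000 trials per row, no true predictors or modifiers, Monte Carlo error about 1 point:

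| Scenario | False interaction at screen | False interaction in final model | Any false term in final model |
|---|---|---|---|
| Independent | 82% | 70% | 99% |
| rho 0.3 | 76% | 64% | 98% |
| rho 0.5 | 72% | 62% | 97% |
| rho 0.7 | 69% | 59% | 96% |
| rho 0.5, HCQ works as designed | 69% | 59% | 95% |
| rho 0.5, N = 200 | 74% | 64% | 98% |

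The mean number of false interactions in the final model is 0.8 to 1.1. The screen column also serves for the section's closing paragraph, if that is read as having no elimination.

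**The interval of a kept interaction.** For an interaction with one degree of freedom, Wald p<0.05 and a 95% interval excluding a ratio of 1 are the same event. Kept by that elimination rule, its interval always excludes 1, and if the true ratio is 1 its coverage is zero. For a 50/50 binary factor the standard error of the log ratio is about sqrt(16/events): 0.496 at 65 events and 0.571 at 49. The estimate must reach exp(1.96 x 0.496) = 2.6 or exp(1.96 x 0.571) = 3.1 to be kept.

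**The case against.** The strongest reply is that the SAP already disclaims inference here. The objective is to explore, the label says exploratory, and SAP 8.1.4 makes secondary intervals descriptive. Nothing in 8.3.5 says a retained term will be declared an effect modifier. All of this stands and limits the severity. It answers multiplicity, however, and not selection. An interval shown only when it excludes 1 does not describe the strength of evidence, whatever it is called.

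Several stronger statements that a reader might infer are not supported:

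- **A flat 70%.** This needs independent factors. The list has near duplicates: CDAI with SDAI, markers in continuous and categorical form, two shared-epitope codings. Entry at anti-CCP3 of 40 or more should leave two of its four categories nearly empty, and pack-years applies only to current smokers. The effective number of tests is below 32.
- **Every kept interval excludes 1.** This holds for one-degree-of-freedom interactions under the elimination rule. It can fail for multi-level factors such as recruitment method, education or smoking status, where a joint test can be significant while single contrasts are not. It also fails under the closing paragraph's wording: in 400 simulated null trials with independent factors, 33% of included interactions had p of 0.05 or more in the joint model.
- **Main effects stay only if p<0.1.** Those attached to a retained interaction stay regardless.
- **Coverage is nearly nil for any reported term.** Zero coverage is specific to a null term. A real factor fares better: a hazard ratio of 1.3 per SD was reported on average as 1.42-1.49 when kept (400 trials).

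**Conclusion.** The point holds in a limited form. As planned, Objective 6 reports ordinary 95% intervals from a model chosen by p-value among 32 factors and 32 interactions. With no true predictors, N = 144 and about 65 events, at least one false HCQ effect modifier appears in the final model in roughly 60-70% of trials. It appears in about 70-80% at the screen, or if no elimination is done. Where in those ranges the trial sits depends on a correlation that the documents do not state, but every scenario run gave a majority. The size is little changed if HCQ works as designed (59%) or if 200 had been enrolled (64%), both at rho 0.5.

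This does not touch the primary analysis, and the documents do not present Objective 6 as confirmatory. It is a cheap improvement to an exploratory output.

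**What to change.** In Table 13:

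1. Make the main Objective 6 output one table of all 32 single-factor hazard ratios and all 32 treatment-by-factor hazard-ratio ratios, with 95% intervals and no selection. The preliminary models that supply them are already planned. Without selection each interval keeps its ordinary meaning, and readers can see that 1.6 of 32 null interactions would be expected to reach p<0.05.
2. If the selected model is also shown, say which of the section's two inclusion rules was used and label the model post-selection. Repeat the whole selection in bootstrap samples (say 1,000) and report how often each term is kept. Attach no ordinary 95% intervals or p-values to it.
3. A Benjamini-Hochberg rule at 5% for naming modifiers is optional. It departs from the stated no-adjustment policy and costs substantial power. Its first cut-off is 0.05/32 = 0.0016 (z = 3.16), so for a 50/50 binary factor the estimated ratio would have to reach about exp(3.16 x 0.496) = 4.8 at 65 events or exp(3.16 x 0.571) = 6.1 at 49, against 2.6 and 3.1 now. A lone modifier with a 50% chance of passing p<0.05 would have about an 11% chance of passing that first cut-off.

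The cost is SAP wording, some extra programming and a less clear-cut selected model. No new data are needed.

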3.3 Description of Secondary Endpoints

3.3.1 Secondary Efficacy Endpoints

1. Time to development of clinically-apparent RA as defined in Section 2.1, *Primary Objective*.
2. Time to development of a swollen joint(s) that is (are) consistent with RA-like synovitis.
3. Development of clinically-apparent RA by 12 months, where clinically-apparent RA is defined in Section 2.1, *Primary Objective*.
4. Development of a swollen joint(s) that is (are) consistent with RA-like synovitis by 12 months, where synovitis is determined by joint exam.
5. Trends in disease activity during the treatment period (i.e. Baseline through Week 52) will be evaluated over time using multiple indices:
 - Physician assessed tender joint count
 - Physician assessed swollen joint count
 - DAS28-CRP score
 - Clinical Disease Activity Index (CDAI)
 - Routine Assessment of Patient Index Data 3 (RAPID-3)
6. Trends in disease activity during the post-treatment follow-up period (Week 52 through Month 36) will be evaluated over time using multiple indices (as noted in above).
7. Trends in patient self-reported evaluations of joint pain, stiffness and swelling will be evaluated over the treatment period (i.e. Baseline through Week 52). The following endpoints are of interest:
 - Total number of painful joints
 - Total number of stiff joints
 - Total number of swollen joints
 - Number of painful joints in the hands, in the wrists, in the feet
 - Number of stiff joints in the hands, in the wrists, in the feet
 - Number of swollen joints in the hands , in the wrists, in the feet
8. Trends in patient self-reported evaluations of joint pain, stiffness and swelling will be evaluated over the post-treatment follow-up period (Week 52 through Month 36). See specific endpoints noted above.
9. Trends in patient-reported outcomes (PRO) for physical, mental and social health (collected via NIH Patient-reported Outcomes Measurement Information System (PROMIS) instrument Profile 29 v2.0) will be evaluated over the treatment period (i.e. Baseline through Week 52).

10. Trends in PRO for physical, mental and social health will be evaluated over the post-treatment follow-up period (Week 52 through Month 36).

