8.3.1.2 Secondary Efficacy Analyses

All secondary analyses will be conducted in an exploratory fashion with p-values and confidence intervals presented as descriptive statistics with no adjustments for multiple comparisons. Tests will be two-sided and interval estimates will be generated at the 95% confidence level. All efficacy analyses will be repeated using the PP population.

The KM estimates for the two arms will be compared using the log-rank test, and survival at 12 months will be compared using methods analogous to those described for the primary efficacy analysis. The two arms will also be compared after control of appropriate covariates using a Cox proportional hazards model. The modeling will also evaluate the relationship between time to onset of clinically-apparent RA (or IA) and covariates such as site, method of recruitment, age, sex, race, baseline characteristics, genetic and environmental factors, and biomarkers.

Treatment group comparisons of longitudinal changes in secondary efficacy endpoints, including disease activity scales, subject self-evaluation scores, and patient reported outcome scores (See Section 3.3.1, *Secondary Efficacy Endpoints*) will be evaluated using repeated measures random regression models. Models will be fit to allow piece-wise fixed-effect for time during the 12-month treatment period and during the subsequent follow-up period through 36 months. A random slope and intercept will be fit for each subject assuming an unstructured covariance matrix. Additional models may be developed to evaluate the relationship of endpoints with appropriate covariates.

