5.4. Per Protocol Population

The Per Protocol (PP) population will be defined as those participants in the mITT population who receive at least 80% of the assigned study treatment regimen with no substantive deviations from protocol procedures that would impact evaluation of efficacy.

A data review panel that will include the Protocol Chair ([name]) and participants from DAIT and Rho, Inc., will evaluate deviations from the protocol including, for example, violations of entry criteria, departures from assigned treatment regimen, use of prohibited therapy or HCQ prescribed outside of the study, failure to complete study visits, or to complete visits within the specified visit windows. The participant ID numbers will be replaced with randomly generated ID numbers for the PP population review.

The ARA08 study conducted an interim analysis in April 2022 as part of the regularly scheduled DSMB review. The Interim Statistical Analysis Plan is provided in Appendix 14.1. Due to the evidence of futility in the interim analysis results, the DSMB recommended that the ARA08 study stop early, and that the treatment assignments be released to the participants. Since the ARA08 study treatment assignments will be unmasked prior to database lock, the data review panel evaluation of the participants to include and exclude from the PP population will take place after the treatment assignments have been unmasked.

Levels of HCQ analyzed from serum samples taken during the study treatment period will not be used in the masked data review panel's evaluations of deviations from the protocol. The panel may exclude participants from the PP population if protocol deviations would be expected to impact the primary efficacy endpoint. Primary and secondary efficacy analyses may be replicated on the PP population.

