8.1.4. Multiple Comparisons/Multiplicity

This study has a single primary analysis to be tested at $\alpha=0.05$. Consequently, no adjustments for multiplicity are needed for Type I error protection.

The secondary efficacy analyses are considered to be supportive with p-values and confidence intervals presented as descriptive measures of strength of evidence rather than formal statistical inference. Therefore, no multiplicity adjustments are needed for this study.

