Participants use the Participant Self-Reported Joint Symptoms assessment to identify painful, stiff, and swollen joints. These data are used to count the number of (1) painful, (2) stiff, and (3) swollen joints, as well as the count of (4) painful, (5) stiff, and (6) swollen joints in the hands, wrists, and feet.

Table 14: Estimands of Study Objective 7

Estimand Label	Variable
Secondary 7.1	Number of self-reported painful joints at each clinic visit
Secondary 7.2	Number of self-reported stiff joints at each clinic visit.
Secondary 7.3	Number of self-reported swollen joints at each clinic visit
Secondary 7.4	Number of self-reported painful joints in the hands, wrists, and feet at each clinic visit
Secondary 7.5	Number of self-reported stiff joints in the hands, wrists, and feet at each clinic visit
Secondary 7.6	Number of self-reported swollen joints in the hands, wrists, and feet at each clinic visit
Population: mITT	IES Policy: All available study data will be included.

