Population Level Summary: At each planned clinic visit, the number, and percent of individuals with self-reported joint symptoms will be computed by treatment arm, and separately for those with and without a prior study-confirmed diagnosis of CL- RA. Among those with symptoms, mean, median, min and max # of affected joints will also be reported. Summary statistics will also be plotted over time to gain a better understanding of trends.	Analysis: At Week 52 and Month 36/EOS, Mann-Whitney U statistics will be used to compare joint counts between treatment arms, separately for those with and without a diagnosis of CL-RA. Because the distributional characteristics of these variables are unknown, we cannot prespecify the planned analysis strategy. However, in this population, it is reasonable to expect there will be excess # of participant visits where no joint symptoms are reported. If this is the case, it may appropriate to fit a longitudinal zero-inflated negative binomial model with the number of involved joints as the dependent variable and treatment arm as the primary fixed effect. Important additional fixed effects to consider would include prior CL-RA diagnosis at time of assessment (Y/N), study day (or visit), treatment period (on study drug vs off study drug), duration on study treatment, and interaction terms for treatment arm, prior CL-RA diagnosis, and study day (or visit). Heterogeneous random participant effects could be included in the model per the methods of Zhu et al [4], and relevant covariates included in the regression on the covariance matrix will be determined. T-tests for the maximum likelihood estimates of the model parameters could be used to determine the significance of the parameters to the model.
Note: Modeling will be exploratory and only initiated if descriptive analyses suggest interesting trends.	

8.3.7. Study Objective 8

Study Objective 8 is to explore underlying immune responses over time in the early natural history of RA development and in response to HCQ therapy through measurement of a variety of biomarkers. Endpoints will be laboratory test results from mechanistic specimens collected at specified clinic visits during the study.

Table 15: Estimands of Study Objective 8

Estimand Label	Biomarkers and immune response variables
Secondary 8.1	Levels of anti-CCP3 over time
Secondary 8.2	Levels of IgM-RF over time
Secondary 8.3	Levels of hsCRP over time

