Population Level Summary: At each planned clinic visit, the number, mean (SD), median, min, and max score will be computed by treatment arm, and separately for those with and without a prior study-confirmed diagnosis of CL- RA. Summary statistics will also be plotted over time to gain a better understanding of trends.	Analysis: At Week 52 and Month 36/EOS, Mann-Whitney U statistics will be used to compare scores between treatment arms, separately for those with and without a diagnosis of CL-RA. If data are consistent with a Gaussian distribution, the data may be analyzed using a repeated measure mixed regression model with the scale score variable at each visit as the dependent variable and treatment arms as the primary fixed effect. Important additional fixed effects to consider would include prior CL-RA diagnosis at time of assessment (Y/N), study day (or visit), treatment period (on study drug vs off study drug), duration on study treatment, and interaction terms for treatment arm, prior CL-RA diagnosis, and study day (or visit). Random participant effects may include random intercepts and/or slopes for each participant
Note: Modeling will be exploratory and only initiated if descriptive analyses suggest interesting trends.	

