12. CHANGES TO THE ANALYSES PLANNED IN THE PROTOCOL

- Protocol section 8.3.1.2 states "All efficacy analyses will be repeated using the PP population." We have modified this plan for secondary efficacy analyses. PP analyses maybe conducted at the discretion of the study team if warranted by results of the mITT analyses.
- Protocol section 8.3.1.1 states "The primary analysis ignores the possible impact of within-family correlation. The propensity to progress to RA could be more similar within families than between families or across individuals in the population, in which case observations in this study would not be independent. Due to operational difficulties in linking family members, we expect to have incomplete information on familial clustering, so we will not be able to account for this potential correlation in the primary analysis. Because families tend to be small and not all family members will be eligible or willing to participate, we anticipate the impact of clustering to be small. We will, however, perform sensitivity analyses to assess the potential impact of clustering. We are asking participants if they have FDRs who are participating. If the proportion who answer affirmative is small, the impact of clustering is likely to be minimal. In addition, participants have the option of linking their study records with those of their relatives. If family clusters are identified through this process, we can estimate the treatment effect from a marginal Cox model for clustered data using the method of Lee, Wei, and Amato [178] and compare these to estimates derived from the usual Cox model assuming independent observations. We could also compare estimates for the risk of developing RA derived from logistic regression models fit using generalized estimating equations under difference assumptions about the within-family correlation structure; independent versus exchangeable [179]."

Upon review of the data collected in ARA08 regarding members of the same family participating in ARA08, it was discovered that no participants reported having an FDR who was also participating in the study. As a result, sensitivity analyses to assess the impact of family clustering will not be performed.

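### The committed between-arm tests of symptoms and disease activity are split by CL-RA diagnosis, a post-randomization outcome, so they do not estimate HCQ's effect on symptoms

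*SAP*

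**What the plan says.** SAP 8.3.6 sets out Objective 7: whether HCQ relieves RA symptoms or delays their onset. Table 14 names the mITT population and states "IES Policy: All available study data will be included". Its committed inference, at Week 52 and Month 36/end of study, is that "Mann-Whitney U statistics will be used to compare joint counts between treatment arms, separately for those with and without a diagnosis of CL-RA".

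Table 16 (physician joint counts) uses the same sentence. Table 17 (DAS28-CRP, CDAI, RAPID-3 and three PROMIS scores) says "Mann-Whitney U statistics will be used to compare scores between treatment arms, separately for those with and without a diagnosis of CL-RA". In all three tables the longitudinal models are exploratory, depend on what the descriptive results show, and list prior CL-RA diagnosis as a fixed effect to consider.

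The protocol planned something else. Section 3.3.1 says "Trends in patient self-reported evaluations of joint pain, stiffness and swelling will be evaluated over the treatment period", with parallel endpoints for disease activity and PROMIS and for post-treatment follow-up. Section 8.3.1.2 assigns "Treatment group comparisons of longitudinal changes in secondary efficacy endpoints, including disease activity scales, subject self-evaluation scores, and patient reported outcome scores" to repeated-measures random regression models, and states no split by CL-RA and no CL-RA term. Protocol 8.5.5 requires the SAP to note major changes. SAP Section 12 cites 8.3.1.2 and says "We have modified this plan for secondary efficacy analyses", but that entry covers only the per-protocol repeats. The other entry concerns family clustering.

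**The concern.** Diagnosis of CL-RA happens after randomization and is the outcome the drug is intended to prevent. Splitting by it breaks the randomized comparison whenever HCQ changes who is diagnosed.

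- **The benefit is hidden.** Symptoms avoided because RA was prevented show up only when whole arms are compared. Within a stratum that benefit is removed by construction.
- **The sign can reverse.** The RA-free HCQ group gains prevented cases, who may carry more symptoms than people never destined for RA. The HCQ group with RA keeps only cases that arose despite treatment, who may be more severe. Both shifts make HCQ look harmful.

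The test sentence also says only that a diagnosis exists, whereas the summary column refers to a prior, study-confirmed one. If the test means ever diagnosed, the Week 52 comparison would condition on later events.

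At stake are the stated evidence for Objective 7 and the between-arm tests for protocol secondary endpoints 5 to 10.

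**Working it through.** **The plan's own figures.** Protocol 8.1 assumes exponential failure with 50% vs 25% CL-RA at 3 years. Hazards: -ln(0.50)/3 = 0.231 and -ln(0.75)/3 = 0.096, ratio 2.41 (stated 2.4). Power with 80 per arm, logit Wald: difference ln(3) = 1.0986; SE = sqrt[1/(80×0.25) + 1/(80×0.1875)] = 0.3416; power = Φ(1.0986/0.3416 − 1.96) = 0.8955 (stated 90%). The design risks therefore reproduce.

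**Number of tests.** 6 self-reported counts + 2 physician counts + 6 scores = 14 variables. With 2 times and 2 strata this gives 56 tests, none across whole arms.

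**Stratum make-up.** The interim SAP reports 144 randomized, about 72 per arm.

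- Month 36: with CL-RA, 72×0.50 = 36 placebo vs 72×0.25 = 18 HCQ; without, 36 vs 54. Prevented cases among RA-free HCQ participants: (0.50 − 0.25)/0.75 = 33%.
- Week 52: risks 1 − 0.5^(1/3) = 20.6% and 1 − 0.75^(1/3) = 9.1%. Prevented cases: (0.206 − 0.091)/0.909 = 12.6%.

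**Illustrative effect on the tests.** The documents give no joint-count distribution, so these inputs are assumptions. RA occurs when a standard normal liability exceeds a threshold c, set by each arm's risk. The joint count is Poisson with mean 2·exp(0.6U), multiplied by m if RA is present. U has correlation ρ with liability. HCQ acts only by preventing RA. With a = 0.6,

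E[exp(aU) | no RA] = exp(a²/2)·Φ(c − aρ)/Φ(c).

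Worked case, Month 36, ρ = 0.4, m = 2.5 (c = 0 placebo, 0.6745 HCQ; 2·exp(0.18) = 2.394):

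- No RA: 2.394×Φ(−0.24)/0.50 = 1.94 placebo; 2.394×Φ(0.4345)/0.75 = 2.13 HCQ; difference +0.19.
- RA: 7.12 placebo, 7.95 HCQ; difference +0.83.
- Whole arm: 4.53 placebo, 3.59 HCQ; difference −0.94.

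All settings with m = 2.5, as HCQ minus placebo. The last column is the share of 4,000 simulated trials, 72 per arm, in which the planned Mann-Whitney test found HCQ significantly worse (nominal 2.5%).

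| Visit | ρ | Whole arm | No RA / RA | HCQ worse, no RA / RA |
|---|---|---|---|---|
| Month 36 | 0 | −0.90 | 0.00 / 0.00 | no shift |
| Month 36 | 0.4 | −0.94 | +0.19 / +0.83 | 6.5% / 8.1% |
| Month 36 | 0.8 | −0.94 | +0.33 / +1.93 | 14.1% / 25.1% |
| Week 52 | 0 | −0.41 | 0.00 / 0.00 | no shift |
| Week 52 | 0.4 | −0.52 | +0.10 / +0.84 | 4.0% / 4.3% |
| Week 52 | 0.8 | −0.61 | +0.21 / +2.25 | 7.4% / 10.5% |

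**Sensitivity.**

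- Treated RA with m = 1.2, Month 36: whole arm −0.12 to −0.13; strata from 0.00 / 0.00 to +0.33 / +0.93.
- Symptom SD 0.3 to 0.9 in place of 0.6 (m = 2.5, ρ = 0.4, Month 36): no RA +0.09 to +0.34, RA +0.33 to +1.69, whole arm −0.81 to −1.19.
- No HCQ effect on RA: all contrasts null, 4.2% to 5.7% rejections.
- A different latent model, with 58 per arm at Month 36 (20% loss) and HCQ preventing RA but having no effect at all on counts: the whole-arm test rejects in 4.8% to 5.3%. At a correlation of 0.5 the stratified tests reject in 10.8% (with CL-RA) and 10.9% (without), with HCQ looking worse in both.

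**Separate minor point.** SAP 8.4.2 computes DAS28-CRP only where a real-time hsCRP sample was taken. Under Protocol 6.5, Week 24 and Months 18, 24 and 30 take a real-time sample only when a swollen joint is found, and the Time of Diagnosis visit takes only a sample for future testing. Read literally, DAS28-CRP at those four visits is limited to participants with a swollen joint, and it is not computed at diagnosis. Baseline, Week 52 and Month 36 are unaffected.

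**The case against.** The strongest reply is about weight. SAP 8.1.4 presents secondary "p-values and confidence intervals presented as descriptive measures of strength of evidence rather than formal statistical inference", and SAP 8.4 labels Tables 16 and 17 exploratory. The summaries by arm at each visit can be read as including whole-arm results, so the randomized contrast may still be visible descriptively. All of this stands and limits the severity. It does not supply a whole-arm test for Table 14, which serves a named secondary objective.

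The bias also needs HCQ to change who gets RA, and SAP 5.4 reports: "Due to the evidence of futility in the interim analysis results, the DSMB recommended that the ARA08 study stop early". Without an effect on RA there is no distortion. Futility evidence makes the 50% vs 25% scenario less plausible but does not prove there is no effect, and the tests target the wrong quantity either way.

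The split has a rationale. After CL-RA the protocol stops study drug and refers the participant to care, so later symptoms may reflect outside treatment. A whole-arm comparison is thus a treatment-policy quantity that mixes treated RA with RA-free participants. That supports keeping a descriptive split, not making it the only test.

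The percentages depend on assumptions. Adding 50% structural zeros among RA-free participants (the SAP expects excess zeros) cuts the no-RA figures at Month 36 to 2.9% and 4.6% (ρ = 0.4, 0.8), but leaves the RA stratum at 7.5% and 23.9%. The whole-arm Mann-Whitney has limited power: about 29% with m = 2.5 and about 5% with m = 1.2, rising to 49–52% with the added zeros.

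Time to IA is tested between whole arms (Objectives 3 and 5), but that is onset of examiner-found synovitis, not a symptom count or activity score. Finally, the absence of a CL-RA term in Protocol 8.3.1.2 is read from silence, and that section allows further covariate models. Its stated comparison is nevertheless between treatment groups.

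**Conclusion.** The concern holds. Each committed between-arm test in Tables 14, 16 and 17 conditions on the trial's own primary outcome, and none compares the randomized arms. If HCQ prevents RA, these tests hide the resulting symptom benefit. They reverse its sign when RA liability and symptoms are positively related. At Month 36 under the design risks and the assumed joint counts (m = 2.5), a whole-arm benefit of about 0.9 joints becomes a contrast of zero to +0.33 without RA and zero to +1.93 with RA. The direction follows from the structure. The size is illustrative, since the symptom mean, spread, RA multiplier and correlation are not in the documents. The change from Protocol 8.3.1.2 is not recorded in SAP Section 12. Because the analyses are secondary or exploratory with descriptive p-values, this should be fixed but does not affect the primary result.

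**What to change.** In Tables 14, 16 and 17, make the treatment comparison the whole mITT arm regardless of CL-RA status. Use either Mann-Whitney at Week 52 and Month 36 or the protocol's random regression model without a CL-RA term. State that this is a treatment-policy comparison that includes symptoms after diagnosis and outside treatment. Keep the split by CL-RA as description without between-arm p-values, and define whether it means diagnosed before the visit. Record the departure from Protocol 8.3.1.2 in SAP Section 12.

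For the minor point, compute DAS28-CRP at Week 24, Months 18, 24 and 30 and Time of Diagnosis from any available core-outcome hsCRP, whether real-time or stored for future testing.

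The cost is SAP wording and a few table shells. No new data are needed: joint counts and scores are already collected, and the stored hsCRP samples are already within Secondary 8.3.
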